6.6.3. Plasma biomarkers

Blood samples for exploratory analysis of plasma biomarkers relevant to AD ($A\beta_{1-40}$, $A\beta_{1-42}$, inflammatory markers, and other markers of interest) will be collected from all patients at baseline (Visit 2), Week 52, and Week 97 (or final study visit) (see Study Plan in Table 2).

These samples will support characterization of the PD effects of AZD3293 on plasma biomarkers, which have not previously been studied in this patient population. The samples will also enable exploratory evaluation of as-yet-unrecognized plasma biomarkers relevant to the diagnosis and prognosis of AD.

The vendor and methodology to analyze the plasma samples will be chosen prior to database lock, given the rapid technological development in this field.

Detailed sample collection and handling procedures are provided in the Laboratory Manual.

Plasma aliquots for future analysis will be retained for up to 15 years from the date of the last patient's last visit or for a shorter period if local regulations and/or ethical review boards (ERBs) /IRBs impose shorter time limits, at a facility selected by the Sponsor or its designee.

For blood sample volumes, see Section 7.1.

6.7. Pharmacogenetics

A blood sample will be obtained at screening for mandatory APOE genotyping.

An optional sample will be collected and stored for future exploratory genetic research from patients who have given specific consent.

Samples will be collected, labeled, stored and shipped as detailed in the Laboratory Manual. The samples for future exploratory genetic research from consenting patients may be retained for up to 15 years or for a shorter period if local regulations and/or ERBs/IRBs impose shorter time limits, at a facility selected by the Sponsor or its designee. If a patient does not consent to the optional genetic research, the blood sample will be discarded after the mandatory APOE genotyping is performed.

For blood sample volumes, see Section 7.1.

6.8. Pharmacogenomics

Blood samples for future pharmacogenomics research will be collected at baseline (Visit 2), Week 52, and Week 97 (or final study visit) (see Study Plan in Table 2) from patients who have given consent for this optional sampling.

Samples will be collected, labeled, stored and shipped as detailed in the Laboratory Manual. The samples may be retained for up to 15 years from the date of the last patient's last visit or for a

shorter period if local regulations and/or ERBs/IRBs impose shorter time limits, at a facility selected by the Sponsor or its designee.

For blood sample volumes, see Section 7.1.

6.9. Health economics

Health economics variables included in this study to address an exploratory objective are the changes from baseline (Visit 2) to Week 104 in the RUD-Lite and EQ-5D-5L scores. The results of analyses of these variables may not be included in the Clinical Study Report, but may be described in supplementary reports as appropriate.

6.9.1. RUD-Lite

The RUD Lite is a short version of Resource Utilization in Dementia (RUD; Wimo and Winblad 2003) interview to assess formal resource utilization of patients with dementia as well as informal resource use (ie, time caregivers spend assisting the patient) during a specific time period. These data make it possible to estimate costs of dementia care from a societal perspective. The administration of the RUD Lite interview takes approximately 10 minutes and captures the following dimensions with regard to the patient: long-term living accommodation, temporary changes in living situation (eg, respite care), and healthcare utilization to include hospital care, emergency room care, practitioner visits, and other resource use (eg, home healthcare, day care, care-related transportation). In addition, the interview assesses time spent by the study partner providing care for the patient in the form of basic activities of daily living (eg, eating, grooming, dressing), instrumental activities of daily living (eg, shopping, food preparation, managing financial matters), and safety surveillance, as well as any time missed from work for caregiving responsibilities if the study partner is still working.

A baseline version of the RUD-Lite questionnaire, given at the initial assessment, inquires about all dimensions of resource utilization over the previous 30 days. The follow-up version of the questionnaire, administered at all subsequent assessments, assesses patient resource use since the last visit and caregiver time over the previous 30 days.

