3.2.4. Study Plan

The Study Plan is described in Table 2 below.

Table 2. Study Plan (D5010C00009)

Study procedure ^a	Screening	Period ^b	Double-blind treatment period															ED ^d	F/U			
Visit number	V1	V2 ^c	V3	V4	V5	V6	V7	V8	V9	V10	V11	V12	V13	V14	V15	V16	V17	V18	V19	V20		V21
Study week			1	4						39					$71^{\rm f}$			91	97	104		108-110 ^g
Tolerance interval for Visit			±3	±3						±7		±10	±7	±7	±7	±7	±7	±7	±7	±10		
(days)																						
Informed consent	X																					
Demographics	X																					
Medical /psychiatric History	X																					
Prior/concomitant treatments	X	X	X	X	X	X	X	X	X	X	X	X	X	X	X	X	X	X	X	X	X	X
Inclusion/exclusion criteria	X	X																				
NIA-AA criteria review	X										X								X		X	
FAQ		X						X				X				X				X	X	
ADCS-ADL		X						X				X				X				X	X	
CDR ^h	X							X				X				X				X	X	
MMSE	X					X		X				X				X				X	X	
RBANS	X										X								X		X	
ADAS-Cog ₁₃		X				X		X				X				X				X	X	
NPI		X						X				X				X				X	X	
Letter & Category Fluency, Digit		X						X				X				X				X	X	
Symbol-Coding tests																						
EQ-5D-5L (patient)		X					X				X					X				X	X	
RUD-Lite		X					X				X					X				X	X	
MRI ⁱ	X											X								X	X	
Florbetapir F 18 Amyloid PET	X																			X	X	
Lumbar puncture ^j	X											X							X		X	
Blood sample for plasma AZD3293 and AZ13569724 PK ^k				X^{l}			X ^m			X ^l	X ^l			X^{m}				X ⁿ			X	
Blood sample for plasma biomarkers ^o		X										X							X		X	

Study procedure ^a	Screening	Double-blind treatment period															ED ^d	F/U				
Visit number	V1	V2 ^c	V3	V4	V5	V6	V7	V8	V9	V10	V11	V12	V13	V14	V15	V16	V17	V18	V19	V20		V21
Study week			1	4	7	13	19	26	32 ^f	39	45	52	58 ^f	65	71 ^f	78	84 ^f	91	97	104		108-110 ^g
Tolerance interval for Visit			±3	±3	±7	±7	±7	±7	±7	±7	±7	±10	±7	±7	±7	±7	±7	±7	±7	±10		
(days)																						
Blood sample for APOE genotyping ^p	X																					
Blood sample for pharmacogenetics ^q	X																					
Blood samples for pharmacogenomics ^q		X										X							X		X	
Laboratory tests ^r	X	X		X	X	X		X		X		X		X		X		X		X	X	
Urine drug screen	X																					
Physical, neurological examinations	X	X		X ^s		X		X ^s		X ^s		X		X ^s		X ^s		X ^s		X	X	
Comprehensive eye examination ^t		X										X								X	X	
Skin examination ^u		X				X						X				X				X	X	
Vital signs ^v	X	X	X	X	X	X	X	X		X	X	X		X		X		X	X	X	X	X
Height	X																					
Body weight	X	X				X		X				X				X				X	X	

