- Visits at Weeks 32, 58, 71, and 84 will be conducted by telephone and may include either the patient or the study partner, or both, as appropriate. The patient or study partner may be required to visit the clinic within ±1 week of Week 32 (Visit 9), Week 58 (Visit 13), Week 71 (Visit 15), or Week 84 (Visit 17) for drug dispensing.
- Patients who complete study treatment at Week 104 or who discontinue study treatment and withdraw early should participate in a follow-up visit (Visit 21), 4 to 6 weeks after the last dose of study treatment. The follow-up visit (Visit 21) is required for patients who discontinue study treatment but remain in the study and continue to participate in scheduled visits. Patients who have completed 104 weeks of study treatment and consent to continue into the extension study, Study AZFD, are not required to complete the follow-up visit (Visit 21).
- The CDR should always be administered to the study partner first and then to the patient; the study partner and patient must be interviewed separately. The assessments should be performed at the same time of day at each visit, if possible.
- The MRI should be performed during screening and done prior to lumbar puncture in those individuals enrolled via CSF.
- Post-baseline CSF samples for patients in the longitudinal sub-study should be collected 2 to 3 hours post-dose. Lumbar punctures should be scheduled at approximately the same time of day at all visits to avoid the known circadian variation in CSF amyloid levels. If a post-baseline lumbar puncture cannot be obtained because of procedural complications or patient issues, it will not be considered a protocol violation.
- Two blood samples for AZD3293 and AZ13569724 PK analysis will be collected just after arrival at and just prior to departure from the clinic at Week 4 (Visit 4), Week 45 (Visit 11), and Week 91 (Visit 18). One blood sample for PK analysis will be collected at Week 19 (Visit 7), Week 39 (Visit 10), and Week 65 (Visit 14) or as soon as possible after treatment discontinuation (if it occurs before Week 91).
- A phone call will be made approximately 1 business day before the clinic visit to remind patients to hold the morning dose of study treatment on the day of the visit and to bring the dose to the clinic.

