11.6. Calculation or derivation of health economic variables

Changes in RUD-Lite and EQ-5D-5L scores at each post-baseline timepoint will be calculated as the post-baseline value minus the baseline value (Visit 2).

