12.2.6. Health economics

For the RUD-Lite, the individual item responses and the total study partner time spent in assisting the patient, as well as changes from baseline in these variables, will be summarized by treatment group and time point using descriptive statistics.

For the EQ-5D-5L and EQ VAS responses and changes from baseline will be summarized by treatment group and time point using descriptive statistics.

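### RUD-Lite patient resource-use counts cover 30 days at baseline and a different period at follow-up, yet change from baseline subtracts them unscaled, so constant use shows a spurious within-group rise

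*Protocol*

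**What the plan says.** Protocol Section 6.9.1 describes two versions of the questionnaire. The baseline version "inquires about all dimensions of resource utilization over the previous 30 days". The version used at every later assessment "assesses patient resource use since the last visit and caregiver time over the previous 30 days". Caregiver time thus keeps one window throughout, while patient resource use changes window after baseline.

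Section 11.6 fixes the change score: "Changes in RUD-Lite and EQ-5D-5L scores at each post-baseline timepoint will be calculated as the post-baseline value minus the baseline value (Visit 2"). Section 12.2.6 applies this at item level and plans descriptive summaries, by group and time point, of "the individual item responses and the total study partner time spent in assisting the patient, as well as changes from baseline in these variables". None of these sections mentions a rate or a common time unit.

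Table 2 in Section 3.2.4 schedules the RUD-Lite at Visits 2, 7, 11, 16 and 20 (baseline and Weeks 19, 45, 78 and 104) and at early discontinuation. Section 6.9 gives the status of the endpoint: "Health economics variables included in this study to address an exploratory objective are the changes from baseline (Visit 2) to Week 104". It adds that the results may be left out of the Clinical Study Report.

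**The concern.** A count of events grows with the length of time it covers. If baseline covers 30 days and follow-up covers several weeks or months, follow-up minus baseline mixes the difference in period with any difference in use. A reader of the planned tables would see resource use rise in every group even if nothing had changed. The rise would also differ from visit to visit, because the gaps between assessments differ.

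The protocol does not say which visit counts as the last one: the last at which the RUD-Lite was given, or the last study visit of any kind. The size of the distortion depends on the answer. Section 6.9.1 says the instrument serves to estimate the societal cost of dementia care, and for that the exposure period behind each count has to be known.

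**Working it through.** The protocol states no figure for the RUD-Lite, so there is none to reproduce. The check works from the schedule.

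**Inputs.** Baseline window: 30 days (6.9.1). RUD-Lite weeks: 0, 19, 45, 78, 104 (Table 2). Visits immediately before each follow-up assessment: Visit 6 (Week 13), Visit 10 (Week 39), Visit 15 (Week 71, by telephone) and Visit 19 (Week 97).

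**Formula.** Let D be the days covered at follow-up and R = D/30. With an unchanged rate of use, the expected follow-up count is R times the expected baseline count. The change from baseline, relative to the baseline count, is R − 1. It should be 0.

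| Assessment | From previous RUD-Lite: D | R | R − 1 | From preceding visit: D | R | R − 1 |
|---|---|---|---|---|---|---|
| Week 19 | (19 − 0) × 7 = 133 | 4.43 | +343% | (19 − 13) × 7 = 42 | 1.40 | +40% |
| Week 45 | (45 − 19) × 7 = 182 | 6.07 | +507% | (45 − 39) × 7 = 42 | 1.40 | +40% |
| Week 78 | (78 − 45) × 7 = 231 | 7.70 | +670% | (78 − 71) × 7 = 49 | 1.63 | +63% |
| Week 104 | (104 − 78) × 7 = 182 | 6.07 | +507% | (104 − 97) × 7 = 49 | 1.63 | +63% |

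If telephone visits do not count as visits, the Week 78 window on the second reading runs from Week 65: 13 × 7 = 91 days, R = 3.03, change +203%.

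In units: one practitioner visit every 30 days, throughout, gives computed changes of +3.4, +5.1, +6.7 and +5.1 visits on the first reading.

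**When use does change.** If the true rate is multiplied by r, the computed change is R·r − 1. At Week 104 a true halving gives 0.5 × 6.07 − 1 = +203% on the first reading, which has the wrong sign. On the second it gives 0.5 × 1.63 − 1 = −18%, which has the right sign but is too small.

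**Share due to recall length.** Splitting the interaction equally, the recall part is (R − 1)(1 + r)/2. Its share of the Week 104 change, for assumed values of r, is:

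| r | First reading | Second reading |
|---|---|---|
| 1 | 100% | 100% |
| 1.5 | 78% | 55% |
| 2 | 68% | 42% |
| 3 | 59% | 32% |

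Under this split, recall is more than half of the change whenever r < R. At Week 104 that means r below 6.07 on the first reading and below 1.63 on the second.

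**Between groups.** Write λ_A and λ_P for the follow-up rates per 30 days in an active group and placebo, and λ_0 for the baseline rate, equal in expectation under randomisation. The difference in raw change is (R·λ_A − λ_0) − (R·λ_P − λ_0) = R(λ_A − λ_P). It is zero when the groups do not differ, so the schedule creates no false group difference. It is expressed per window and not per 30 days, however. On the first reading the same difference in rates looks 231/182 = 1.27 times as large at Week 78 as at Week 104.

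**The case against.** The strongest reply concerns consequence. The stated aim is to explore the effect of treatment on resource use, which is a comparison between randomised groups, and Table 2 gives all three groups the same RUD-Lite visits. That stands. A reader might infer that the treatment comparison is biased, but the last step of the working shows that the schedule does not do this. Unequal windows could arise only through irregular timing, such as early-discontinuation or missed assessments, and the documents give nothing with which to size that.

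A second reply concerns scope. A reader might infer that RUD-Lite change as a whole mainly reflects length of recall. The documents do not support that. Caregiver time keeps 30 days at every assessment, and total study partner time is the one aggregate that Section 12.2.6 names. Long-term living accommodation is a state, not a count. Even for the counts, the word mainly is secure only if recall runs from the previous RUD-Lite.

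A third inference would be that sites will read the last visit differently, and that the resulting noise will hide a group difference. The questionnaire's own wording is not in the protocol, raters are trained and certified (Section 9.2), and no variance is available to support the claim. It should not be made.

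Finally, scaling counts to a common period is the kind of derivation often left to the SAP. That would answer the point if the protocol were silent. It is not: 11.6 states the subtraction and 12.2.6 applies it to the item responses. Reporting rates as well is not forbidden, but the rule as written gives the wrong answer.

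**Conclusion.** The point holds for the patient resource-use count items, as a statement about within-group change and comparison across visits. Followed as written, Sections 11.6 and 12.2.6 report a rise when use is constant on either reading of the recall period: +343% to +670% if it starts at the previous RUD-Lite, +40% to +63% if it starts at the immediately preceding visit. Both ranges assume nominal visit weeks and a constant rate of use. The documents do not settle which applies.

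The severity is minor. The endpoint is exploratory, its analysis is descriptive, and no hypothesis test or decision rests on it.

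**What to change.** In Sections 11.6 and 12.2.6, state that each patient resource-use count is expressed per 30 days (count ÷ days covered × 30, with days covered taken from actual assessment dates) before it is summarised or its change from baseline is taken. An unchanged rate then gives a change of 0 at every visit. Caregiver time and living accommodation need no conversion.

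In Section 6.9.1, state that the follow-up recall period for patient resource use runs from the last RUD-Lite administration. The four windows then cover the 104 weeks without gaps. Counted from the preceding visit they would cover 6 + 6 + 7 + 7 = 26 weeks. For forms already completed, days covered should follow the period that the questionnaire actually asked about.

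The cost is two sentences and a one-line derivation. Visit dates are already collected, and no visit or procedure is added.

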6.9.2. EQ-5D-5L

The EQ-5D-5L (patient) provides a single index value for health status and is relevant to a wide range of health conditions and treatments. It is administered to the patient in only a few minutes and consists of 2 pages: the EQ-5D-5L descriptive system and the EQ Visual Analogue scale (EQ VAS). The descriptive system covers 5 dimensions (mobility, self-care, usual activities, pain/discomfort, anxiety/depression) each rated on 5 levels: no problems, slight problems, moderate problems, severe problems, and extreme problems.

The EQ VAS records the patient's estimation of his/her health on a visual analogue scale with endpoints labeled "the best health you can imagine" and "the worst health you can imagine." This information can be used as a quantitative measure of patient health. The EQ-5D-5L asks the patient to mark an "X" on the scale to indicate his/her current health status.

7. BIOLOGICAL SAMPLING PROCEDURES

7.1. Volume of blood

The approximate volume of blood that will be drawn from each patient in this study is shown in Table 6.

Table 6. Volume of Blood to be Drawn From Each Patient

	Assessment	Panel volume (mL)	No. of time points	Total volume (mL)
Safety	Clinical chemistry/Electrolytes	2.5	12	30
	Hematology	2	12	24
	Coagulation	1.8	1	1.8
	Endocrinology	3.5*	3	8.5
	Screening tests	8.5	1	8.5
	Optional/Confirmatory Testing	11	1	11
Pharmacok	inetics			
	AZD3293 and AZ13569724	3	9**	27
Plasma biomarkers		12	3	36
Pharmacog	enetics			
Mandatory APOE genetic sampling		2	1	2
Optional genetic sampling		6	1	6
Pharmacogenomics		5	3	15
Total				169.8

Note: Total volume does not include unscheduled Hepatic testing, early discontinuation, or unscheduled/follow-up visit

7.2. Handling, storage and destruction of biological samples

The samples will be used up or disposed of after analyses or retained for further use as described here.

The results from future analyses will not be reported in the Clinical Study Report but separately in a scientific report and/or scientific publication.

7.2.1. Pharmacokinetic and/or pharmacodynamic samples

Blood and CSF samples collected for PK analysis will be disposed of after the Bioanalytical Report is finalized or 6 months after issuance of the draft Bioanalytical Report (whichever is earlier), unless retained for future analyses.

Incurred sample reproducibility analysis, if any, will be performed alongside the bioanalysis of the test PK samples. The results from the evaluation will not be reported in the Clinical Study Report but separately in a Bioanalytical Report.

^{*3.5} mL collected at screening (Visit 1) and 2.5 mL collected at the other 2 visits (Visit 12 and Visit 20).

^{**}Visits 4, 11, and 18 collects 2 time points. See Section 6.5.1.

Selected PK samples may be used for additional metabolite identification and/or quantification or to investigate any potential dosing issues.

Key blood and CSF samples collected for biomarker analysis may be retained for future investigations. These samples will be retained for a maximum of 15 years following last patient's last visit or for a shorter period if local regulations and/or ERBs/IRBs impose shorter time limits, at a facility selected by the Sponsor or its designee. The results from investigations involving retained samples will be provided in separate reports and not in the Clinical Study Report.

7.2.2. Pharmacogenetic samples

The processes adopted for the coding and storage of samples for genetic analysis are important to maintain patient confidentiality. Samples will be stored for a maximum of 15 years from the date of the last patient's last visit or for a shorter period if local regulations and/or ERBs/IRBs impose shorter time limits, after which they will be destroyed. DNA is a finite resource that may be used up during analyses. Samples will be stored and used until no further analyses are possible or the maximum storage time has been reached.

For all samples, irrespective of the type of coding used, the DNA will be extracted from the blood sample. The DNA sample will be assigned a unique number replacing the information on the sample tube. Thereafter, the DNA sample will be identifiable by the unique DNA number only. The DNA number is used to identify the sample and corresponding data at the at the designated contract laboratory. No personal details identifying the individual will be available to any person

The samples and data for genetic analysis in this study will be single coded. The link between the patient enrollment/randomization code and the DNA number will be maintained and stored in a secure environment, with restricted access. The link will be used to identify the relevant DNA samples for analysis, facilitate correlation of genotypic results with clinical data, allow regulatory audit, and trace samples for destruction in the case of withdrawal of consent when the patient has requested disposal/destruction of collected samples not yet analyzed.

7.3. Labeling and shipment of biohazard samples

The Principal Investigator ensures that samples are labeled and shipped in accordance with the Laboratory Manual for this study and the Biological Substance, Category B Regulations (materials containing or suspected to contain infectious substances that do not meet Category A criteria).

Any samples identified as Infectious Category A materials are not shipped, and no further samples will be taken from the patient unless agreed with sponsor and appropriate labeling, shipment and containment provisions are approved.

7.4. Chain of custody of biological samples

A full chain of custody is maintained for all samples throughout their lifecycle.

The Principal Investigator at each center keeps full traceability of collected biological samples from the subjects while in storage at the centre until shipment or disposal (where appropriate) and keeps documentation of receipt of arrival.

The sample receiver keeps full traceability of the samples while in storage and during use until used or disposed of or until further shipment and keeps documentation of receipt of arrival.

The sponsor keeps oversight of the entire lifecycle through internal procedures, monitoring of study sites and auditing of external laboratory providers.

Samples retained for further use are registered in the system during the entire lifecycle.

